5. ADVERSE EVENTS

5.1 DEFINITIONS

Adverse Event (AE): any untoward medical occurrence in a patient or clinical study subject.

Serious Adverse Event (SAE): any untoward and unexpected medical occurrence or effect that:

- Results in death
- Is life-threatening refers to an event in which the subject was at risk of death at the time of the event; it does not refer to an event which hypothetically might have caused death if it were more severe
- Requires hospitalisation, or prolongation of existing inpatients' hospitalisation
- Results in persistent or significant disability or incapacity
- Is a congenital anomaly or birth defect

Medical judgement will be exercised in deciding whether an AE is serious in other situations. Important AEs that are not immediately life-threatening or do not result in death or hospitalisation but may jeopardise the subject or may require intervention to prevent one of the other outcomes listed in the definition above, may also be considered serious.

5.3 REPORTING PROCEDURES

There are no expected Adverse Events throughout this study. In the unexpected occurrence of an AE, the adverse event will be reported. Depending on the nature of the event the reporting procedures below will be followed.

5.3.1 Non serious AEs

All such events, whether expected or not, should be recorded.

5.3.2 Serious AEs

An SAE form will be completed and faxed to the Chief Investigator within 24 hours. New onset diabetes, and hospitalisations for elective treatment of a pre-existing condition do not need reporting as SAEs.

All SAEs will be reported to the Sponsor where in the opinion of the Chief Investigator, the event was:

- 'related', ie resulted from the administration of any of the research procedures;
 and
- 'unexpected', ie an event that is not listed in the protocol as an expected occurrence

Reports of related and unexpected SAEs should be submitted within 15 days of the Chief Investigator becoming aware of the event, using the NRES SAE form for non-IMP studies. The Chief Investigator must also notify the Sponsor of all SAEs.

Local investigators should report any SAEs as required by their Local Research Ethics Committee, Sponsor and/or Research & Development Office.

6. STUDY TEM AND VISIT ORGANISATION

We anticipate operating at least 2 surveillance teams per country / region (ie at least 10 teams total); the surveillance teams will rotate through the selected surveillance sites over the course of study. An expedited approach with greater initial effort may be used if appropriate, to achieve the same objective.

The typical composition (human resource) of the surveillance team is summarized in **Table 2**. The study equipment that will be used in summarized in **Table 3**.

Each surveillance team will work in a station based approach to maximise efficiency (**Figure 1**). The estimated duration of each station is shown; the surveillance health assessment is anticipated to take ~90 mins per person. We anticipate that each surveillance team will assess 25-40 participants per day; we thus anticipate screening 250-300 people per day across all sites (ie ~60,000 people per year, ~160,000 by Q1 2021).

[figure not shown]
Table 2. Typical composition of each surveillance team. Additional staff will be available for transportation and security, as required in respective local contexts.

Type of staff	Number	Job responsibility			
		Overall responsibility for the team			
Medical officer	1	Report on the clinical and laboratory data collected			
		Clinical guidance and counselling of participants			
Co-ordinator	1	Co-ordinate the team and oversee data collection			
Co-ordinator	ı	Implement quality control protocols			
		Registration and consent (1 Pax)			
		 Administer participant questionnaires (2 tables → 2 Pax) 			
Research Assistants /	5	 Anthropometry and blood pressure (1 Pax) 			
nurses		Assist Medical officer in clinical review (1 Pax)			
		Carry out household listing (afternoon activity, all)			
Phlebotomist	1	Collection of blood samples and urine samples			
		12 lead ECG (1 Pax)			
		Retinal photography (1 Pax)			
Laboratory technicians	4	Spirometry (1 Pax)			
		Analyse blood samples (1 Pax)			
		Process biological samples for storage (afternoon, all)			

 Table 3. Provisional equipment list for the surveillance project.

Measurement	Device	Number		
1. Core equipment (NCD "toolkit"; one toolkit per site)				
Height	Seca Wall Mounted Tape Measure	1		
Weight	Salter Electronic Scale	1		
Tape measure	Plastic tape measure	1		
Blood pressure	Omron device or Aneroid sphygmomanometer + stethoscope	1		
Glucometer	To be selected as a device in routine local use	1		
Tablet	7" Fusion5 Android Tablet or equivalent	1		
2. Special equipment (one	set per surveillance team)			
Weight & bioimpedance	OMRON BF511 (clinically validated)	2		
Blood pressure	Omron M3 IT or equivalent			
Spirometry	MIR: Minispir or Spirobank Smart			
12 lead ECG	GE: Mac800 or equivalent			
Retinal photography	Remedio: Fundus on a Phone or equivalent	1		
Blood tests: HbA1c	SD Biosensor: Multicare HbA1c	1		
Blood tests: Lipids	SD Biosensor: Lipidocare	1		
Tablets	7" Fusion5 Android Tablet or equivalent			
Printer	TBC	1		
Centrifuge	Remi C854/6	2		
Fridge	Local vendor, 4C	1		

Figure 1. Station based approach to NCD surveillance.

Sample storage

We will collect ~20mls of blood and 10mls of urine from participants during the surveillance exercise. Aliquots of whole blood, serum, plasma, and urine will be stored at -80C for future quantification of biomarkers for cardiovascular and metabolic health (eg measurement of NTpro-BNP as a measure of heart function, or insulin/C-peptide for glucose metabolism), and as a resource for future molecular epidemiological studies to investigate the mechanisms underpinning the development of CVD, T2D, and other complex disease that are of importance to South Asian populations (including but not limited to: obesity, cancer, dementia, COPD, chronic kidney disease). The molecular epidemiological research will use a range of strategies including, but not limited to: genome sequencing and genotyping, studies of genomic regulation (eg quantification of DNA methylation), molecular profiling of serum and urine (eg by targeted and untargeted metabolomics, or proteomics). Data and all appropriate documentation will be stored for a minimum of 10 years after the completion of the study, including the follow-up period. Whilst some laboratory assays on stored samples will be done in South Asia, we anticipate that the majority of assays will be carried out in the UK or other country with relevant technology.

Samples collected will be stored in both South Asia and the UK (ie samples storage will be split between the two geographic regions) to help ensure long-term sample integrity and preservation. Material and transfer agreements has been arranged between Imperial College London and institutions collecting the samples. Sample storage in the UK will be at the LOLIPOP biorepository, London and / or the UK Biocentre in Milton Keynes. Evidence of agreement to store samples has been obtained from the above-mentioned entities.

Quality control and data analysis

Quality control

The surveillance teams, comprising research assistants, laboratory technicians, physicians and co-ordinators will be trained to follow standardized protocols in each country/region. Their training modules will include interviewing techniques, ethics and specific instructions for each of data (demographic, socio-economic, food security, behavioural risk factors, medication and lifestyle practices, physical measurement and collection of biological samples etc.). Revalidation of the research teams in study procedures will be done at regular intervals during the study to ensure continued high-quality data collection that is harmonized across sites. Standardized operating procedures will be established for all data collection procedures.

Questionnaires will be translated into the languages appropriate to the communities, and back-translated to ensure adequacy of translation. Equipment used for physical and biological

measurement will be regularly calibrated using appropriate controls/standards. The data management team will review the data collected and provide daily feedbacks on inaccuracy and missing data, and will adopt data-driven approaches to monitoring data quality (eg checks on biases in data entry, logical inconsistencies, internal correlations, digit preference, measurement drift or bias between machines and observers). If necessary, we will also consider re-assessing a random subset comprising up to 2% of the study participants, and/or re-testing a subset of biological samples to provide additional quality control data. To the extent possible, an attempt will be made to use data collection methods that are "field-friendly" (e.g., devices that are portable and can also give immediate readings and do not require additional laboratory analysis), culturally-acceptable and minimally-invasive in order to reduce subject attrition and improve logistical feasibility.

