At each study site, governmental census data and other available household listings will be used, supported by house-house visits, to fully enumerate and identify the resident population. House-to-house visits will be done by the local primary care worker, in partnership with the research team. The purpose and potential benefits (personal and societal) of the surveillance will be explained. The research team will then obtain demographic details for the adult population of each household. People eligible and consenting to take part in the surveillance study will be asked to attend a nearby health facility in the fasting state, for the surveillance health assessment. Explanations of the project will be provided in writing and using videos, available in relevant South Asian languages, and supported by bilingual translators. We will also engage the community elders (eg teachers, employers, religious leaders) as trusted third parties, to support and facilitate engagement of the community in the study. Based on previous experience with population studies in these communities, participation rates are expected to exceed >70%; the availability of household enumeration data will enable participation to be monitored in detail, including by age, gender and major socio-economic groups.

Study procedures

Participants will be asked to attend in the morning after an overnight fast (water only after midnight). All participants will complete a structured assessment by trained members the dedicated research team, in five complementary domains: i. Registration and consent; ii. Questionnaire; iii. Physical measurements; iv. Biological samples and v. Clinical reporting. All study procedures implemented represent well established tools, that are validated for assessment of NCDs in population studies. The procedures will be carried out by trained research staff, using equipment and protocols that are standardized between countries and surveillance sites.

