- i) Registration and consent. Written, informed consent will be obtained from all participants for data collection, and inclusion in the research. Informed consent will include permission for the data and samples collected to be used for NCD research, including data sharing with national and international bodies concerned with prevention and control of T2D and CVD, as well as for molecular epidemiological research. Consent will be facilitated using videos (available in major South Asian languages) and supported by bilingual translators. A unique study ID will be allocated to each participant.
- ii) **Questionnaire**. An interviewer administered health and lifestyle questionnaire will be used to collect information on behavioral risk factors (smoking, alcohol habit, physical activity and fruits/vegetables consumption), personal and family medical history, medications, socioeconomic status and knowledge of NCDs. The questionnaire is founded on the extended WHO

STEPS questionnaire that is widely used in global NCD surveillance,¹⁷ but adapted for use in South Asia, including through incorporation of additional questions. The interviewer administered questionnaires will be translated into locally relevant languages, and supported by graphics representations to facilitate collection of high quality data.

- iii) **Physical measurements**. Including: a) Anthropometry (height, weight, waist and hip circumference, and bio-impedance for body fat composition); b) Blood pressure by digital device; c) Cardiac evaluation by 12 lead ECG to identify arrhythmia, LVH and previous myocardial infarction; d) Retinal photography for assessment of retinal disease, including hypertensive and diabetic retinopathy; and e). Respiratory evaluation by spirometry to assess for smoking/environment-related lung injury.

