7. STATISTICS AND DATA ANALYSIS

The key study indicators are based on the WHO NCD Global Monitoring Framework (Appendix 1). Therefore, we will follow the operational definition of the indicators, method of estimation, and guidelines for data disaggregation (by sex/socio-demographic stratifiers) proposed in the framework. As we will use a multistage sampling approach, appropriate sample weight will be estimated and used during the descriptive analysis.

Data will be analysed using appropriate statistical software (eg STATA, SPSS). Continuous variables will be assessed for normality, and non-normally distributed variables will be transformed as appropriate or will be assessed using non-parametric tests if appropriate. The data and samples collected will enable both cross-sectional and longitudinal analyses, and thus to define the prevalence and incidence of clinical outcomes of interest respectively. We will quantify the relationship between the clinical outcomes of interest, and potential underlying exposures (lifestyle, environmental, genetic) risk factors using regression techniques. For the assessment of relationship between a continuous primary and secondary outcome we will carry out mixed models analysis of covariance (e.g., BP, HbA1c, blood cholesterol, serum creatinine) etc. Mixed models logistic regression will be used to assess the association between explanatory and categorical outcome variables (e.g., T2D, CVD, hypertension, hypercholesterolemia). Regional differences within and between countries will also be explored. Statistical significance will be inferred at P<0.05, using techniques (eg Bonferroni) to control for multiple comparisons where appropriate. Power estimates for analyses of cross-sectional and longitudinal outcomes data are summarized in **Tables 4 and 5**.

Table 4. Power calculations for cross-sectional analyses. Results are expressed as i. the precision with which the prevalence for a clinical outcome of interest can be quantified and ii. the odds ratios (OR) detectable for association between a clinical outcome and an underlying exposure (exposure prevalence 20%, power 90%, P<0.05). Precision and power estimates are provide overall (N~160,000 people), at the level of the country (M~30,000 people), or at the level of the site (N~750 people). The table also summarized precision and power for low (~1%), intermediate (5-10%) and high frequency (~20-30%) outcomes of interest.

			Precision	OR detectable		

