Appendix 1. WHO Primary and secondary indicators for NCD prevention and control

The relevant core NCD surveillance indicators from the WHO Global Monitoring Framework, that will be directly captured in our surveillance study are as follows:

Domain	Indicators
Mortality and morbidity	 Unconditional probability of dying between ages of 30 and 70 from cardiovascular diseases, cancer, diabetes or chronic respiratory diseases
Behavioral risk factors	 Total (recorded and unrecorded) alcohol per capita consumption within a calendar year in litres of pure alcohol, as appropriate, within the national context Age-standardized prevalence of insufficient physically active persons aged 18+ years (defined as less than 150 minutes of moderate-intensity activity per week, or equivalent) Age-standardized prevalence of current tobacco use among persons aged 18+ years
Biological risk factors	 Age-standardized prevalence of raised blood pressure among persons aged 18+ years (defined as systolic blood pressure ≥140 mmHg and/or diastolic blood pressure ≥90 mmHg) and mean systolic blood pressure Age-standardized prevalence of raised blood glucose/diabetes among persons aged 18+ years (defined as fasting plasma glucose concentration ≥ 7.0 mmol/l (126 mg/dl) or on medication for raised blood glucose) Age-standardized prevalence of overweight and obesity in persons aged 18+ years (defined as body mass index ≥23 kg/m² for overweight and body mass index ≥ 28 kg/m² for obesity)
Behavioural risk factors	Age-standardized prevalence of persons (aged 18+ years) consuming less than five total servings (400 grams) of fruit and vegetables per day
Biological risk factors	 Age-standardized prevalence of raised total cholesterol among persons aged 18+ years (defined as total cholesterol ≥5.0 mmol/l or 190 mg/dl); and mean total cholesterol concentration
Drug and counseling	 Proportion of eligible persons (defined as aged 40 years and older with a 10-year cardiovascular risk ≥30%, including those with existing cardiovascular disease) receiving drug therapy and counselling (including glycaemic control) to prevent heart attacks and strokes Proportion of people with hypertension receiving drug therapy and counselling Proportion of people with diabetes receiving drug therapy and counselling

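### The only glucose device listed is a locally chosen glucometer, against the promise of standardised equipment, so a between-model offset could be confounded with locality in the diabetes indicator

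*Protocol*

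**What the plan says.** Section 4 (Study procedures) commits the survey to "using equipment and protocols that are standardized between countries and surveillance sites". Under biological samples it plans fasting glucose, lipids and HbA1c from venous blood, using validated near-patient assays.

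Table 3 in section 6 is headed provisional and has two tiers.

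- **Core kit, "one toolkit per site".** The glucometer entry reads "To be selected as a device in routine local use". The blood-pressure entry reads "Omron device or Aneroid sphygmomanometer + stethoscope".
- **Special set, one per surveillance team.** It names one HbA1c analyser and one lipid analyser. For blood pressure it lists "Omron M3 IT or equivalent". It contains no glucose device.

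Appendix 1 gives the raised-glucose/diabetes indicator as "defined as fasting plasma glucose concentration ≥ 7.0 mmol/l (126 mg/dl) or on medication for raised blood glucose". Section 7 adopts the operational definitions of the WHO framework and adds: "Regional differences within and between countries will also be explored".

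**The concern.** A prevalence based on a fixed cut is sensitive to calibration, because many people lie close to the cut and a small proportional offset carries some of them across it. If the meter model follows locality, that offset is aligned with the regions and sites being compared. The survey data alone cannot then tell a device difference from a true difference in diabetes prevalence. Enlarging the sample narrows the interval around the biased value, and design weights correct for selection, not for measurement.

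At stake are the raised-glucose/diabetes prevalence by site and region as Appendix 1 defines it, and the comparisons of that indicator within and between countries.

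**Working it through.** **1. The texts side by side.** Section 4 says equipment is common to countries and sites. Table 3 leaves the glucose device to local routine. Neither tier lists another device that measures glucose. Analytes with a named team analyser (HbA1c, lipids) keep the section 4 promise; glucose does not.

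**2. The plan's own precision.** Table 4 gives half-widths for diabetes at 20% prevalence. The formula 1.96·√(p(1−p)/n) with p = 0.20 gives:

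| n | Recomputed | Table 4 |
|---|---|---|
| 160,000 | 0.196% | 0.2% |
| 30,000 | 0.453% | 0.5% |
| 750 | 2.86% | 2.9% |

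The figures reproduce. They describe sampling error only.

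**3. Effect of a meter offset (illustration).** The documents give no device bias and no glucose distribution, so these inputs are assumptions: log-normal fasting glucose, log-SD s between 0.20 and 0.35, a share p truly at or above 7.0 mmol/l, and a meter reading high by a proportion b. The observed share is

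1 − Φ( z(1−p) − ln(1+b)/s ).

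Example with p = 0.20, b = 0.05, s = 0.20: z = 0.8416 and ln(1.05)/0.20 = 0.2440. The difference is 0.5977, so the observed share is 27.5%, a shift of 7.5 points.

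| True share | b | Shift, s = 0.35 | Shift, s = 0.20 |
|---|---|---|---|
| 10% | +1% | 0.5 points | 0.9 points |
| 10% | +5% | 2.7 points | 5.0 points |
| 20% | +1% | 0.8 points | 1.4 points |
| 20% | +2% | 1.6 points | 2.9 points |
| 20% | +5% | 4.1 points | 7.5 points |

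At 20%, an offset of about 0.3% (s = 0.20) to 0.6% (s = 0.35) already equals the 0.45-point country half-width.

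**4. Allowing for medication.** Step 3 puts all prevalence on the glucose cut, but Appendix 1 also counts people on medication, and their status does not depend on the meter. Let a fraction m of the 20% be classified by medication; the documents give no value, so m is an assumption. The unmedicated share of the population is u = 1 − 0.20m. Among them, q = 0.20(1−m)/u lie above the cut, and the shift is u·{1 − Φ(z(1−q) − ln(1.05)/s) − q}.

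| m | u | q | Shift at +5%, s = 0.35 to 0.20 |
|---|---|---|---|
| 0 | 1.00 | 0.200 | 4.1 to 7.5 points |
| 0.25 | 0.95 | 0.158 | 3.4 to 6.3 points |
| 0.50 | 0.90 | 0.111 | 2.6 to 4.8 points |
| 0.75 | 0.85 | 0.059 | 1.6 to 2.9 points |

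The shift shrinks as m rises. In these examples it stays above the 0.45-point half-width.

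**The case against.** Several points count against a stronger reading.

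- **Use of the local meter is inferred.** A reader might conclude that survey glucose will be read on the site glucometer. The protocol does not say so. It describes venous blood and validated near-patient assays, and the site kit duplicates the team's scale, blood-pressure device and tablet, so it is not plainly the survey instrument set. However, height and the tape measure appear only in the site kit, and no other glucose device is listed. The role of the kit is therefore unclear. This objection stands, and it is why the point is conditional.
- **One model per country is not stated.** The entry is still to be filled, so confounding with locality is a possibility that the rule permits, not an established fact.
- **There is a second route to diabetes.** HbA1c is measured on one named analyser, and an oral glucose tolerance test in a subset is meant to validate classification by HbA1c. Table 4 does not tie its diabetes row to the glucose definition, so not every regional comparison of diabetes is exposed. The Appendix 1 indicator does not use HbA1c and remains exposed.
- **Quality control is more than a check for drift.** Section 6 promises regular calibration against controls or standards and monitoring for bias between machines, and section 4 stores aliquots for external quality control. Calibration to a common standard would reduce an absolute offset. But no comparison between glucose models is specified, and re-testing of samples is to be considered only if necessary.
- **Blood pressure.** A reader might infer from the aneroid entry that hypertension prevalence carries a device bias too. The documents do not support this. Section 4 specifies "Blood pressure by digital device", each team carries its own digital monitor, and the aneroid option appears only in the site kit.

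**Conclusion.** The conflict over glucose is real in the current text: a common device is promised, and the only one listed is chosen locally. If that device produces the survey readings, an offset between models may be confounded with locality in the Appendix 1 diabetes indicator. Under the assumptions shown, a 5% high reading moves a prevalence of 10-20% by about 3 to 7 points (2.7 to 7.5 in the table) when all prevalence rests on the glucose cut, and by less once medicated people are set aside. These are illustrative biases set beside a sampling half-width; they do not estimate the error of any actual meter. The quality-control measures and HbA1c reduce the exposure without closing it. That the list is provisional makes correction easy but does not resolve the conflict.

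The blood-pressure entry needs clarification only; no bias is shown there. Confidence is medium, because use of the local glucometer for survey data is inferred.

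**What to change.** 1. In Table 3, list one glucose device and strip type in the per-team set, used in all five regions, as is already done for HbA1c and lipids. Failing that, pre-plan a comparison of each local model against a common reference.
2. Record device model and serial number with each reading.
3. State which equipment tier produces study data.
4. Reconcile the aneroid entry in the site kit with the digital device specified in section 4.

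The cost is small: an amendment to a list still marked provisional, and one meter model for at least 10 teams (at least two per region, five regions). The downside is that some regions would have to import meters and strips that they do not routinely stock. The fallback avoids that import but adds a comparison exercise for every local model.
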